9.2 Definitions

All sites of disease should be followed as either target or non-target lesions, as categorized at baseline. All measurable lesions up to a maximum of 2 lesions per organ or 5 lesions in total, representative of all involved organs should be identified as target lesions, while all other lesions (either additional measurable lesions or non-measurable lesions) should be classified as non-target lesions. In cases where a target lesion is believed to be present and is faintly seen but too small to measure, a default value of 5 mm should be assigned. To ensure comparability, the baseline radiology/scans and subsequent radiology/scans to assess response should be performed using identical techniques (eg, scans performed immediately following bolus contrast administration should be made with a standard volume of contrast, the identical contrast agent, and preferably the same scanner). The same method, radiological or physical, should be employed and assessed by the same individual on each occasion, when possible.

9.3 Measurable disease

Measurable lesions are defined as those that can be accurately measured in at least one dimension (longest diameter to be recorded) as >10 mm with CT scan (with minimum slice thickness no greater than 5mm, or 10mm caliper measurement by clinical exam, or 20mm by chest X-ray). All tumor measurements must be recorded in millimeters (or decimal fractions of centimeters).

Pathological lymph nodes may also be considered as target or non-target lesions. To be considered pathologically enlarged and measurable (target lesion), a lymph node must be ≥ 15 mm in short axis when assessed by CT scan (CT scan slice thickness recommended to be no greater than 5 mm). Lymph nodes with a short axis ≥ 10 mm but < 15 mm

should be considered non-target lesions. Lymph nodes that have a short axis < 10 mm are considered non-pathologic and should not be recorded. The short axis measurement of any lymph node that is considered a target lesion should continue to be recorded regardless if the node progresses to below 10 mm. This may prevent the sum of lesions from being zero even if complete response criteria are met, since a normal lymph node is defined as having a short axis of < 10 mm. In rare circumstances, when a target lymph node is believed to be present and is faintly seen but too small to measure, a default value of 5 mm should be assigned.

9.4 Non-measurable disease

All other lesions (or sites of disease), including small lesions (longest diameter < 10 mm or pathological lymph nodes with ≥ 10 to < 15 mm short axis) as well as truly non-measurable lesions. Lesions considered truly non-measurable include: leptomeningeal disease, ascites, pleural/pericardial effusions, lymphangitis cutis/pulmonis, inflammatory breast disease, abdominal masses (not followed by CT or MRI). For bone and cystic lesions, please refer to the RECIST criteria (version 1.1, 2009).

9.5 Target lesions

All measurable lesions up to a maximum of five lesions total (and a maximum of two lesions per organ) representative of all involved organs should be identified as target lesions and recorded and measured at baseline. Target lesions should be selected on the basis of their size (lesions with the longest diameter) and their suitability for accurate repeated measurements (either by imaging techniques or clinically). A sum of the diameters for all target lesions (longest for non-nodal lesions, short axis for nodal lesions) will be calculated and reported as the baseline sum diameters (LD). The baseline sum diameters will be used as reference by which to characterize the objective tumor response.

9.6 Non-target lesions

All other lesions (or sites of disease) should be identified as non-target lesions and should also be recorded at baseline. Non-target lesions include measurable lesions that exceed the maximum numbers per organ or total of all involved organs as well as non-measurable lesions. It is possible to record multiple non-target lesions involving the same organ as a single item on the case record form (e.g. “multiple enlarged pelvic lymph nodes” or “multiple liver metastases”). Measurements of these lesions are not required, but the presence or absence of each should be noted throughout follow-up.

9.7 Guidelines for evaluation of measurable disease

All measurements should be taken and recorded in metric notation using a ruler or calipers. All baseline evaluations should be performed as closely as possible to the beginning of treatment and never more than 4 weeks before the beginning of the treatment.

The same method of assessment and the same technique should be used to characterize each identified and reported lesion at baseline and during follow-up. Imaging-based evaluation is preferred to evaluation by clinical examination when both methods have been used to assess the antitumor effect of a treatment.

Clinical lesions. Clinical lesions will only be considered measurable when they are superficial (e.g., skin nodules and palpable lymph nodes). In the case of skin lesions, documentation by color photography, including a ruler to estimate the size of the lesion, is recommended.

Chest x-ray. Lesions on chest x-ray are acceptable as measurable lesions when they are clearly defined and surrounded by aerated lung. However, CT is preferable.

Conventional CT and Magnetic Resonance Imaging. Conventional CT and MRI should be performed to obtain images of 5 mm or less slice thickness.

Tumor markers. Tumor markers alone cannot be used to assess response. If markers are initially above the upper normal limit, they must normalize for a patient to be considered in complete clinical response.

Cytology, Histology. These techniques can be used to differentiate between partial responses (PR) and complete responses (CR) in rare cases (e.g., residual lesions in tumor types, such as germ cell tumors, where known residual benign tumors can remain). The cytological confirmation of the neoplastic origin of any effusion that appears or worsens during treatment when the measurable tumor has met criteria for response or stable disease is mandatory to differentiate between response or stable disease (an effusion may be a side effect of the treatment) and progressive disease.

9.8 Response criteria

Evaluation of target lesions

- Complete Response (CR): Disappearance of all target and non-target lesions including normalization of elevated tumor marker level. Any pathological lymph nodes (whether target or non-target) must have reduction in short axis to < 10 mm. All non-target lymph nodes must be non-pathological in size (< 10 mm short axis). Complete response must be confirmed at a second tumor assessment not less than 4 weeks apart from the assessment at which CR was observed.
- Partial Response (PR): At least a 30% decrease in the sum of LD of target lesions taking as reference the baseline sum LD. Partial response must be confirmed at a second tumor assessment not less than 4 weeks apart from the assessment at which PR was observed.
- Progressive Disease (PD): At least a 20% increase (and an absolute increase of at least 5 mm) in the sum of LD of measured lesions taking as references the smallest sum LD recorded since the treatment started. Appearance of new lesions will also constitute PD. In exceptional circumstances, unequivocal progression of non-target lesions may be accepted as evidence of disease progression.
- Stable Disease (SD): Neither sufficient shrinkage to qualify for PR nor sufficient increase to qualify for PD, taking as reference the smallest sum LD since the treatment started
- Non-CR/Non-PD: Persistence of 1 or more non-target lesions and/or maintenance of tumor marker level above the normal limits.

Evaluation of non-target lesions

- Complete Response (CR): Disappearance of all non-target lesions and normalization of tumor marker level
- Incomplete Response/ Stable Disease (SD): Persistence of one or more non-target lesion(s) and/or maintenance of tumor marker level above the normal limits
- Progressive Disease (PD): Appearance of one or more new lesions and/or unequivocal progression of existing non-target lesions
- Although a clear progression of “non-target” lesions only is exceptional, in such circumstances, the opinion of the treating physician should prevail, and the progression status should be confirmed at a later time by the study chair.
- Note: If tumor markers are initially above the upper normal limit, they must normalize for a patient to be considered in complete clinical response.

9.9 Time point evaluation

At each protocol specified time point, a response assessment occurs. Table 9 provides a summary of this for patients who have measurable disease at baseline. Table 10 provides a summary of this for patients with non-measurable (therefore non-target) disease.

Table 8: Response for measurable disease

Target Lesions	Non-target Lesions	New Lesions	Overall Response	Best Response for this Category also Requires
CR	CR	No	CR	≥ 4 weeks Confirmation
CR	Non-CR/Non-PD	No	PR	≥ 4 weeks Confirmation
CR	Not evaluated	No	PR	
PR	Non-PD or not all evaluated	No	PR	
SD	Non-PD or not all evaluated	No	SD	Documented at least once ≥ 6 weeks from baseline
Not All Evaluated	Non-PD	No	NE	NE
PD	Any	Yes or No	PD	No prior SD, PR or CR
Any	PD*	Yes or No	PD	
Any	Any	Yes	PD	

* In exceptional circumstances, unequivocal progression in non-target lesions may be accepted as disease progression. NE = inevaluable Note: Patients with a global deterioration of health status requiring discontinuation of treatment without objective evidence of disease progression at that time should be reported as “symptomatic deterioration.” Every effort should be made to document the objective progression even after discontinuation of treatment.

Table 9: Response for non-measurable disease

Non-target Lesions	New Lesions	Overall Response
CR	No	CR
Non-CR/Non-PD	No	Non-CR/Non-PD
Not all evaluated	No	NE
Unequivocal PD	Yes or No	PD
Any	Yes	PD

NE = inevaluable a 'Non-CR/non-PD' is preferred over 'stable disease' for non-target disease since SD is increasingly used as endpoint for assessment of efficacy in some trials so to assign this category when no lesions can be measured is not advised.

9.10 Evaluation of best overall response

The best overall response is the best response recorded from the start of the treatment until disease progression/recurrence (taking as reference for progressive disease the smallest measurements recorded since the treatment started). The patient's best response assignment will depend on the achievement of both measurement and confirmation criteria.

Table 10: Response Assignment

Overall Response First Time Point	Overall Response Subsequent Time Point	BEST Overall Response
CR	CR	CR
CR	PR	SD, PD, or PR
CR	SD	SD provided minimum criteria for SD duration met, otherwise, PD
CR	PD	SD provided minimum criteria for SD duration met, otherwise, PD
CR	NE	SD provided minimum criteria for SD duration met, otherwise, NE
PR	CR	PR
PR	PR	PR
PR	SD	SD
PR	PD	SD provided minimum criteria for SD duration met, otherwise, PD
PR	NE	SD provided minimum criteria for SD duration met, otherwise, NE
NE	NE	NE

NE = inevaluable. If a CR is *truly* met at first time point, then any disease seen at a subsequent time point, even disease meeting PR criteria relative to baseline, makes the disease PD at that point (since disease must have reappeared after CR). Best response would depend on whether minimum duration for SD was met. However, sometimes ‘CR’ may be claimed when subsequent scans suggest small lesions were likely still present and in fact, the patient had PR, not CR at the first time point. Under these circumstances, the original CR should be changed to PR and the best response is PR.

Patients with a global deterioration of health status requiring discontinuation of treatment without objective evidence of disease progression at that time should be classified as having “symptomatic deterioration.” Every effort should be made to document the objective progression, even after discontinuation of treatment.

In some circumstances, it may be difficult to distinguish residual disease from normal tissue. When the evaluation of complete response depends on this determination, it is recommended that the residual lesion be investigated (fine needle aspirate/biopsy) before confirming the complete response status.

9.11 Confirmation

To be assigned a status of PR or CR, changes in tumor measurements must be confirmed by repeat assessment at a minimum follow-up interval of 6 weeks after the criteria for response are first met. In the case of SD, follow-up measurements must have met the SD criteria at least once after study entry at a minimum interval of 6 weeks.

9.12 Duration of overall response

The duration of overall response is measured from the time measurement criteria are met for CR or PR (whichever is first recorded) until the first date that recurrent or progressive disease is objectively documented (taking as reference for progressive disease the smallest measurements recorded since the treatment started).

The duration of overall CR is measured from the time measurement criteria are first met for CR until the first date that recurrent disease is objectively documented.

9.13 Duration of stable disease

Stable disease is measured from the start of the treatment until the criteria for progression are met, taking as reference the smallest measurements recorded since the treatment started.

10. STATISTICAL METHODS

10.1 Study design and sample size

This is a single arm, open label, phase II trial to assess the efficacy and toxicity of ramucirumab in patients with pre-treated, advanced bile duct cancer. The primary objective is to evaluate the efficacy of the therapy. The primary endpoint is the progression-free survival (PFS). A maximum of 60 patients will be enrolled in the study at an estimated accrual rate of 2-3 patients per month. The study will monitor for futility and safety so that it will stop early if based on the interim data, it is unlikely the PFS will be better than that estimated from historical data or the study drug is too toxic.

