10. The patient must have adequate coagulation function as defined by International Normalized Ratio (INR) ≤ 1.5 and a partial thromboplastin time (PTT) (PTT/aPTT) $< 1.5 \times$ ULN.). Patients on full-dose anticoagulation must be on a stable dose (minimum duration 14 days) of oral anticoagulant or low molecular weight heparin. If receiving warfarin, the patient must have an INR ≤ 3.0 and no active bleeding (that is, no bleeding within 14 days prior to first dose of protocol therapy) or pathological condition present that carries a high risk of bleeding (for example, tumor involving major vessels or known varices).
11. Because the teratogenicity of ramucirumab is not known, the patient, if sexually active, must be postmenopausal, surgically sterile, or using effective contraception (hormonal or barrier methods).
12. Female patients of childbearing potential must have a negative serum pregnancy test within 7 days prior to enrollment.
13. Patients must sign an Informed Consent and Authorization indicating that they are aware of the investigational nature of this study and the known risks involved.
14. Patient is ≥ 18 years of age on the day of consenting to the study.
15. In the ten patient expanded cohort, patients diagnosed with DNA repair or FGFR genetic aberrations will be enrolled.

EXCLUSION CRITERIA

1. The patient has experienced any Grade 3-4 GI bleeding within 3 months prior to enrollment.

2. Prior therapy with any agent targeting the VEGFR pathway to include bevacizumab, pazopanib, and other anti-angiogenesis inhibitors.
3. The patient has a history of deep vein thrombosis, pulmonary embolism, or any other significant thromboembolism, including portal venous thrombosis (venous port or catheter thrombosis, incidental pulmonary embolism diagnosed on imaging studies or superficial venous thrombosis are not considered “significant”) during the 3 months prior to randomization.
4. The patient has experienced any arterial thromboembolic events, including but not limited to myocardial infarction, transient ischemic attack, cerebrovascular accident, or unstable angina, within 6 months prior to enrollment.
5. The patient has uncontrolled or poorly-controlled hypertension (>160 mmHg systolic or > 100 mmHg diastolic for >4 weeks) despite standard medical management.
6. The patient has a serious or non-healing wound, ulcer, or bone fracture within 28 days prior to enrollment.

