6. TREATMENT PLAN

This is an open-label phase II study. Patients with advanced biliary cancers will be enrolled. All patients must be registered on the M. D. Anderson Cancer Center Clinical Oncology Research (CORE) system prior to initiation of treatment.

This study will enroll up to 60 patients to at MD Anderson Cancer Center. Accrual is projected to be 2.5 subjects per month. If this study proceeds to a future trial for patients with DNA repair gene of FGFR mutations, data obtained from this expanded cohort of 10 patients will be included in final analysis.

This will be an open-label, single arm study with each cycle being 14 days. Ramucirumab will be administered at 8 mg/kg intravenously on day 1 of the cycle. Restaging will be done every 4 cycles (+/- 1week). Treatment will be continued until progression unless other reasons for study discontinuation occur as listed in section 8 “Criteria for Removal from the Study.” Additionally, patients who have therapy interrupted for consolidative therapies (including, but not limited to radiation therapy, radioembolization, and chemoembolization) or at the physician’s discretion, will remain on study for survival analyses.

Table 2: Starting Dose Level

Drug	Dose	Infusion Time	Schedule (in 14-day cycle)
IV Ramucirumab	8 mg/kg	60 min (+/- 5 min)	Day 1

Dosing and Administration

The study drug will be provided by the sponsor and administered in the following order with the specified pre-medications:

- Premedication should be with an IV H₁ agonist, diphenhydramine 50 mg in NS 50 mL IV within 30 minutes prior to treatment
- Ramucirumab 8 mg/kg in NS to final volume of 250 mL IV over 60 minute on day 1 repeated every 14 days

Dose Modifications and Toxicity Management

Dose modifications and treatment delays based on observed drug-related toxicity will be performed as described below. Any toxicity associated or possibly associated with ramucirumab treatment should be managed according to standard medical practice.

Specific adverse events of concern, which may or may not be associated with ramucirumab therapy, include infusion reactions, hypertension, arterial or venous thrombotic events, bleeding (hemorrhagic) events, and proteinuria. These are specified in greater detail below.

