10.2 Primary efficacy endpoint

The primary endpoint is PFS, which is calculated as the time period from the date of treatment start to the date of disease progression or to the date of death, whichever occurs first, or to the last follow-up date if patients are alive without disease progression. It is expected that the median PFS time will be 3 months or more under this study treatment. If the trial continues to accrual of 60 patients and maintains sufficient follow-up to observe 35 events (PD/death) with a median PFS of 3 months, then the 95% credible interval for the median PFS would extend from 2.1 to 4.2 months.

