10.3 Futility monitoring

For futility monitoring, we will monitor PFS using the methods of Thall et al and we will stop enrolling patients to the study if the median PFS is not likely to be longer than that from the historical data, which is around 3 months. Specifically, the trial will be stopped if $Pr(\lambda(E) > \lambda(S) | \text{data from the trial}) < 0.05$, where $\lambda(S)$ is the median PFS for historical patients under conventional care with an inverse gamma distribution $IG(58.25, 171.75)$, which corresponds to a mean of 3 months and a standard deviation of 0.4 month (variance = 0.16), the corresponding 95% CI of (2.32, 3.88) months. The prior for $\lambda(E)$ is assumed to be $IG(2.5625, 4.6875)$, corresponding to a mean of 3 months and a larger standard deviation of 4 (variance=16, the corresponding 95% CI is 0.72-10.67). Futility monitoring will start once 5 patients have been enrolled. Assuming an accrual rate of 2 per month and an additional follow-up of 6 months, the operating characteristics for the futility stopping rule under various scenarios are summarized in Table 11 below, with results based on 5000 simulations.

Table 11: Operating characteristics for futility monitoring

Median PFS (M)	Prob(Stop Early)	Mean No. of Patients (25%, 75%)
6	0.0058	49.5 (50, 50)
4.5	0.0216	49.1 (50, 50)
3	0.1674	44.2 (50, 50)
2	0.855	23.7 (10,37)
1.5	0.9992	12.3 (7, 16)

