10.4 Toxicity monitoring

Unacceptable toxicities will also be monitored closely for the study drug using the method of Thall et al (1995). Denote the probability of unacceptable toxicity by T_E , Unacceptable toxicity will be defined as follows, using the National Cancer Institute’s (NCI) Common Terminology Criteria for Adverse Events (CTCAE) v 4.0. For the purpose of toxicity monitoring, only unacceptable toxicities that occur in the first 28 days (i.e., 2 cycles) will be counted when assessing the stopping boundary. That is, a patient will be classified as not having toxicity if the patient has been treated for 28 days and no unacceptable toxicity has been observed.

- Grade 4 neutropenia lasting ≥ 5 days or Grade 3 or 4 neutropenia with fever and/or infection

- Grade 4 thrombocytopenia (or Grade 3 with bleeding)
- Grade 4 anemia
- Grade 3 or 4 non-hematological toxicity [excluding electrolyte abnormalities, alopecia or grade 3 nausea that is correctable with usual supportive medications]
- Dosing delay greater than 14 days due to treatment-emergent AEs or related severe laboratory abnormalities
- Grade 3 hypersensitivity reaction with premedication (Grade 3 hypersensitivity reaction without premedication is not considered a DLT)
- Grade 4 hypersensitivity reaction with or without premedication
- Drug-related fever \leq Grade 3 will not be considered a DLT.

We assume $T_E \sim \text{beta}(0.3, 0.7)$. We will stop the enrollment if at any point $\Pr(P_E > 0.30 \mid \text{data}) > 0.9$. That is, we will stop the trial if, at any time during the study, we determine that there is more than 90% chance that the unacceptable toxicity rate is more than 30%. This toxicity monitoring rule will be applied after the first 5 patients have been enrolled and evaluated, and then in cohort size of 5. The corresponding stopping boundaries are to stop the trial if (number of patients with unacceptable toxicities / number of patients) $\geq 4/5, 6/10, 8/15, 9/20, 11/25, 13/30, 15/35, 16/40, 18/45$. The operating characteristics (OCs) are listed in Table 12.

Table 12: OCs for unacceptable toxicity monitoring

True Prob(unacceptable tox)	Pr(stop)	mean # Pts (25%, 50%, 75%)
0.1	0.0006	49.97 (50, 50, 50)
0.2	0.0225	49.21 (50, 50, 50)
0.3	0.2215	43.59 (50, 50, 50)
0.4	0.6869	30.12 (15, 25, 50)
0.5	0.9597	17.77 (10, 15, 20)

Multc Lean V2.1 and OneArmTTE Version 4.1.1 were used for the trial design.

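### The plan allows 60 patients, but Tables 11 and 12 and the printed toxicity boundaries were computed for a maximum of 50

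*Combined protocol and SAP*

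**What the plan says.** Three places in the combined protocol and SAP give the maximum as 60:

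- Section 10.1: "A maximum of 60 patients will be enrolled in the study at an estimated accrual rate of 2-3 patients per month".
- Section 6: "This study will enroll up to 60 patients".
- Section 10.2, which introduces the credible interval with: "If the trial continues to accrual of 60 patients".

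Both monitoring rules are worded for the whole study. Section 10.3 says "we will stop enrolling patients to the study if the median PFS is not likely to be longer", and Section 10.4 says "we will stop the trial if, at any time during the study". The toxicity rule starts at 5 patients and is then applied in cohorts of 5. Its printed boundaries are "4/5, 6/10, 8/15, 9/20, 11/25, 13/30, 15/35, 16/40, 18/45".

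The printed operating characteristics are capped at 50. In Table 11 the quartiles are 50 and 50 for medians of 3, 4.5 and 6 months. In Table 12 the quartiles are 50, 50, 50 and the mean is 49.97 at a true rate of 0.1.

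The protocol also has a molecularly selected group. Inclusion criterion 15 in Section 5 reads: "In the ten patient expanded cohort, patients diagnosed with DNA repair or FGFR genetic aberrations will be enrolled". Section 6 adds, on condition that a future trial follows, that "data obtained from this expanded cohort of 10 patients will be included in final analysis". Section 2 reports an initial cohort of 43 enrolled and 42 treated.

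**The concern.** A 60-patient trial that almost never stops early must have a mean sample size near 60 and quartiles of 60. The tables show 49.97 and 50. The stopping probabilities and expected sample sizes that justify the design therefore appear to come from a different design.

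Two gaps follow. With cohorts of 5 and a cap of 60, there would be toxicity looks at 50 and 55, and neither has a printed boundary. No sentence says how the 60 is composed, or whether patients chosen for DNA-repair or FGFR alterations are pooled with unselected patients in either rule. Pooling could matter for futility, because Section 2 reports such alterations in 5 of the 6 patients with prolonged stable disease.

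**Working it through.** **Toxicity: inputs (Section 10.4).** Prior beta(0.3, 0.7); stop if Pr(rate > 0.30 | data) > 0.9; looks every 5 patients. With x events in n patients the posterior is beta(0.3 + x, 0.7 + n − x). The boundary is the smallest x whose posterior probability exceeds 0.9.

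**Boundaries.** The rule returns all nine printed boundaries. For example, 18/45 gives 0.917 and 17/45 gives 0.858. Continued past 45, it gives:

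- n = 50: 20 events gives 0.928 and 19 gives 0.878, so the boundary is 20/50.
- n = 55: 22 events gives 0.938 and 21 gives 0.895, so the boundary is 22/55.

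**Operating characteristics** (exact binomial recursion over cohorts of 5). Each cell is Pr(stop) / mean N.

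| True rate | Printed Table 12 | Cap 50, looks to 45 | Cap 60, looks to 45 | Cap 60, looks to 55 |
|---|---|---|---|---|
| 0.1 | 0.0006 / 49.97 | 0.0006 / 49.97 | 0.0006 / 59.97 | 0.0006 / 59.97 |
| 0.2 | 0.0225 / 49.21 | 0.0225 / 49.21 | 0.0225 / 58.99 | 0.0226 / 58.98 |
| 0.3 | 0.2215 / 43.59 | 0.2215 / 43.59 | 0.2215 / 51.38 | 0.2327 / 51.29 |
| 0.4 | 0.6869 / 30.12 | 0.6869 / 30.12 | 0.6869 / 33.25 | 0.7263 / 32.94 |
| 0.5 | 0.9597 / 17.77 | 0.9597 / 17.77 | 0.9597 / 18.17 | 0.9753 / 18.05 |

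The cap-50 column equals the printed table to every digit, and the printed quartiles reproduce as well. The fourth column can be checked by hand. If no look is added, every trial that does not stop enrols 10 more patients, so mean N = printed mean + 10 × (1 − Pr(stop)). At 0.3 this is 43.59 + 10 × 0.7785 = 51.38. At 0.4 it is 30.12 + 10 × 0.3131 = 33.25. At a cap of 60 the quartiles at 0.4 become 15, 25, 60 (printed 15, 25, 50).

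**Futility: inputs (Section 10.3).** Historical median ~ IG(58.25, 171.75); experimental prior IG(2.5625, 4.6875); stop if Pr(λ(E) > λ(S) | data) < 0.05; first look at 5 patients; 2 patients per month; 6 months' further follow-up. Assumptions: exponential PFS and a look before each new enrolment. The posterior for the experimental median is IG(2.5625 + events, 4.6875 + ln 2 × total follow-up time). Each cell below is Pr(stop) / mean N, from 20,000 simulated trials with Poisson accrual and a final look.

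| True median (months) | Printed Table 11 | Cap 50 | Cap 60 |
|---|---|---|---|
| 6 | 0.0058 / 49.5 | 0.007 / 49.7 | 0.007 / 59.6 |
| 4.5 | 0.0216 / 49.1 | 0.023 / 49.0 | 0.022 / 58.9 |
| 3 | 0.1674 / 44.2 | 0.165 / 44.2 | 0.169 / 52.5 |
| 2 | 0.855 / 23.7 | 0.862 / 23.7 | 0.899 / 25.0 |
| 1.5 | 0.9992 / 12.3 | 0.999 / 12.3 | 1.000 / 12.3 |

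The printed quartiles at 2 months (10, 37) and 1.5 months (7, 16) reproduce at a cap of 50. Varying the accrual pattern and the final look gives Pr(stop) of about 0.88 to 0.90 at a 2-month median with a cap of 60, and mean N of about 52 to 53 at 3 months. At the 2.5 per month of Section 6, Pr(stop) at 2 months is 0.88 without the final look and 0.90 with it, and mean N at 3 months is about 52 to 53.

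**One Table 11 cell fails on its own terms.** With a cap of 50 and a first look at patient 5, a stop saves at most 45 patients. A Pr(stop) of 0.0058 therefore implies a mean of at least 50 − 0.0058 × 45 = 49.74, but the 6-month row prints 49.5.

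**Would the missing toxicity looks matter in practice?** Section 2 reports 9 grade 3 toxicities and no grade 4 among 42 treated. Suppose all 9 count, each in a different patient, and every later patient has an event. By patient 50 there are at most 9 + 8 = 17 events, against 20 needed. Reaching 22 by patient 55 needs 13 more events in 13 patients. This assumes a pooled count and no qualifying dosing delays beyond those 9.

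**The case against.** The strongest reply is that this is a labelling matter. Prior, cutoff and cohort size are printed, so anyone can extend the rule. Stopping probabilities hardly move, and futility protection at a 2-month median slightly improves. The Section 10.2 credible interval rests on 35 events and is unaffected. The toxicity already reported makes the missing looks nearly irrelevant. All of this stands, and it limits the weight of the point.

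A second reply is that the explicit list ending at 18/45 governs, and that the study-wide phrase only paraphrases the posterior rule. On that reading every printed toxicity stopping probability is right at 60. This is arguable, since the text supports either reading. It does not rescue the printed mean sample sizes, which are wrong for 60 whether looks end at 45 or 55.

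A third reply is that the design is plainly 50 plus a ten-patient expansion. That is a plausible origin, but no sentence says so, limits monitoring to the first 50, or exempts the expansion patients. The reported 43 plus 10 is 53. As 60 is a ceiling, 53 contradicts nothing, but it does not explain the 60 either. If the total is 53, the look at 55 never occurs.

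The question of pooling the selected patients and the 6-month cell in Table 11 are separate matters. They are best settled in the same edit but add no weight to the mismatch.

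**Conclusion.** The point holds. Tables 11 and 12 and the boundary list describe a 50-patient trial, while the plan states 60 in three places.

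For toxicity this is exact, given the printed rule. For futility it rests on exponential PFS and an assumed look before each enrolment, but the agreement at 50 and the printed quartiles leave no real doubt about the cap.

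The main error is in expected enrolment. It is understated by about 8 patients at a true toxicity rate of 0.3 or a 3-month median, and by about 10 when the drug is safe or active. Most of this simply reflects the higher cap. Stopping probabilities differ by at most about 4 to 5 percentage points. The rules can still be run and a changed decision is unlikely. The figures nevertheless need correcting or labelling, because they are the plan's quantitative case for its stopping rules.

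**What to change.** Choose one of two edits:

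1. Label Tables 11 and 12 and the boundary list as computed for, and covering, the first 50 patients only, and say what monitoring applies after that.
2. Restate both tables for 60 and add the boundaries that the stated prior and cutoff imply, 20/50 and 22/55.

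In either case, state in Section 10.1 how the 60 is made up, and in Sections 10.3 and 10.4 whether the ten molecularly selected patients count in each rule. Recheck the mean of 49.5 in the 6-month row of Table 11 at the same time.

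The first option costs a label and one or two sentences. Only the second needs the design software to be rerun. Neither adds patients or procedures.
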